## Inclusion of Minorities:

See the **Targeted/Planned Enrollment Table** for this project. Enrollment targets are based on population estimates of the 2010 US census for the state of Michigan and Washtenaw County (location of UMHS) with some modifications. For Michigan; 78.9% White, 14.2% African-American, 0.6% Native American, 2.4% Asian, 0% Hawaiian & Pacific Islander, 1.5% Other Race, 2.3% Two or More Races; 4.4% Hispanic/Latino, 95.6% Not Hispanic or Latino. For Washtenaw County; 74.5% White, 12.7% African- American, 0.3% Native American, 7.8% Asian, 0% Hawaiian & Pacific Islander, 1.5% Other Race, 2.3% Two or More Races; 4.0% Hispanic/Latino, 96% Not Hispanic or Latino. Hispanic/Latino residents tend to be recent immigrants and younger than the population average, so we project enrollment of fewer Hispanic/Latino participants than the Hispanic/Latino proportion of state/county population. Similar considerations apply to Asians. Some epidemiologic evidence suggests that PD is less prevalent among African-Americans, so we project fewer African-American enrollees than the proportion of African-Americans in our state/county. The Education and Outreach Core will assist with Minority recruitment.

## Project III: Inclusion of Children

#### Justification for Exclusion of Children:

No children will be included. PD occurs predominantly in late-life and, indeed, the risk of developing PD increases with increasing age. In rare cases with clear familial inheritance, the onset of the disease may occur in the 30's and 40's, but there is no evidence of clinical PD in children. Therefore, the research topic to be studied is not relevant to children.

## Planned Enrollment Report

Study Title:

Project III: a4b2\* nAChRs, Gait, and Balance in PD

Domestic/Foreign:

Domestic

Comments:

Pasial Catagorian					
Racial Categories	Not Hispanic or Latino		Hispanic or Latino		Total
	Female	Male	Female	Male	
American Indian/Alaska Native	0	0	0	0	0
Asian	0	0	0	0	0
Native Hawaiian or Other Pacific Islander	0	0	0	0	0
Black or African American	1	0	0	0	1
White	28	38	1	1	68
More than One Race	0	0	0	0	0
Total	29	38	1	1	69

Study 1 of 1

2.1 Preface

Falls and other abnormalities of gait and balance are common in Parkinson's disease (PD), are largely levodopa unresponsive, and are major contributors to morbidity and mortality. The central theme of the University of Michigan Udall Center is that degeneration of basal forebrain (BF) and pedunculopontine (PPN) cholinergic projections, in the context of degraded striatal motor control, contributes significantly to PD gait and balance deficits. Our preclinical work identifies attentional deficits, secondary to loss of cortical cholinergic afferents, as a key mechanism through which cholinergic deficits contribute to impaired gait and balance. The goal of this pilot target engagement/pharmacodynamic clinical study is to assess $\alpha 4\beta 2^*$ nicotinic cholinergic receptors (nAChRs) as a therapeutic target for improving gait, balance, and attentional capacity in PD.

To demonstrate the $\alpha 4\beta 2^*$ nAChRs are appropriate therapeutic targets inPD, it is necessary to study key pharmacokinetic-pharmacodynamic features of $\alpha 4\beta 2^*$ nAchR in the context of the degenerating, hypocholinergic PD brain, a pathologic environment in which they may exhibit unique features. This personalized medicine approach focuses our studies on hypocholinergic PD subjects. We will assess $\alpha 4\beta 2^*$ nAChR features using Positon Emission Tomography (PET) imaging with the $\alpha 4\beta 2^*$ nAChR ligand [¹⁸F]flubatine, subacute administration of the $\alpha 4\beta 2^*$ nAChR partial agonist varenicline (VCN), and laboratory measures of gait, balance, and attention. We will perform a pharmacodynamics study with subacute VCN administration to determine if $\alpha 4\beta 2^*$ nAChR stimulation improves laboratory measures of gait function, postural control, and attentional function in hypocholinergic PD subjects.

2.2 Scope of the analyses

These analyses will assess the efficacy and safety of varenicline in comparison with placebo, addressing the primary and secondary objectives of the study.

3 Study Objectives and End points

3.1 Study Objectives

Primary Objective

• To assess the effects of pharmacologic α4β2* nAChR activation on laboratory measures of gait function and postural control in PD subjects with cholinergic deficits.

Secondary Objectives

• To assess the effects of pharmacologic $\alpha 4\beta 2^*$ nAChR activation on a measure of attentional function (SAT; sustained attention test) in PD subjects with cholinergic deficits.

Exploratory Objectives

• To assess the effects of pharmacologic $\alpha 4\beta 2^*$ nAChR activation on additional measures of motor, cognition, and behavior in PD subjects with cholinergic deficits.

3.2 End points

All efficacy end points are assessed at the end of each treatment period (days 22 and 64).

3.2.1 **Primary Efficacy End points**

- JERK (postural measure based on time-based derivative of lower trunk accelerations)
- Gait speed under normal pace and no dual task conditions

3.2.2 Secondary Efficacy End points

• Sustained attention test (SAT)

3.2.3 **Exploratory Efficacy End points**

- Movement Disorder Society Unified Parkinson's Disease Rating Scale, part III (MD-UPDRSIII; "on" state)
 - o Total score
 - Postural instability and gait disorder (PIGD) subscore
- Gait measures
 - Gait speed under fast pace and no dual task conditions
 - Gait speed under normal pace and dual task conditions minus gait speed under normal pace and no dual task conditions
 - Gait speed under fast pace and dual task conditions minus gait speed under fast pace and no dual task conditions
 - Cadence under normal pace and no dual task conditions
 - Cadence under fast pace and no dual task conditions
 - Mean stride length under normal pace and no dual task conditions
 - Mean stride length under fast pace and no dual task conditions
 - $\circ~\%$ coefficient of variation (CV) stride length under normal pace and no dual task conditions
 - %CV stride length under fast pace and no dual task conditions
 - Mean stride time under normal pace and no dual task conditions
 - Mean stride time under fast pace and no dual task conditions
 - %CV stride time under normal pace and no dual task conditions
 - %CV stride time under fast pace and no dual task conditions
 - Mean stride width under normal pace and no dual task conditions
 - Mean stride width under fast pace and no dual task conditions
 - %CV stride width under normal pace and no dual task conditions
 - %CV stride width under fast pace and no dual task conditions
- Postural measures
 - Mean sway velocity
 - Root mean square sway distance (Sway RMS)
 - Timed Up and Go (iTUG)
- Cognitive measures
 - Montreal Cognitive Assessment (MoCA) score
 - Wechsler Adult Intelligence Scale (WAIS-III) Digit Symbol score
 - California Verbal Learning Test (CVLT) Short Term Memory score
 - CVLT Long Term Memory score
 - CVLT Recognition score
 - o Delis-Kaplan Executive Function System (D-KEFS) Stroop III (interference) score
 - o D-KEFS Sorting total score
 - D-KEFS Verbal Fluency Letters total score
 - o D-KEFS Verbal Fluency Animal score
 - Judgment of Line Orientation (JOLO) score
 - Trail Making Test (TMT) 4 score
 - Distractor Sustained Attention Test (dSAT) score
- Behavioral measures
 - Geriatric Depression Scale (GDS)
 - Questionnaire for Impulsive-Compulsive Disorders in PD (QUIPs)

[figure not shown]
4 Study Methods

4.1 General Study Design and Plan

This study is a single-center, randomized placebo-controlled double-blind crossover study of VCN in participants with PD to assess its effects on measures of gait, balance, and cognition. Participants were randomized 1:1 to one of two treatment sequences: placebo followed by VCN 0.5 mg b.i.d., or

VCN followed by placebo. Participants received an initial 0.25 mg dose or equivalent placebo following baseline evaluations and were monitored for 4 hours after initial study medication administration with total daily dose or equivalent placebo escalated over the next 2 days. Treatment periods were 3 weeks in duration and interrupted by a 3-week washout period. Participants underwent a standard evaluation at baseline, at the end of the first treatment period (week 3 [day 22]), at end of the washout period-beginning of the second treatment period (week 6 [day43]), and at the end of the second treatment period (week 9 [day 64]).

The schema below describes the main elements of the study design:

4.2 Inclusion-Exclusion Criteria and General Study Population

- 4.2.1 Inclusion Criteria
 - 1. PD diagnosis will be based on the United Kingdom Parkinson's Disease Society Brain Bank Research Center (UKPDSBRC) clinical diagnostic criteria. We will enrich the cohort by recruiting subjects at modified Hoehn and Yahr stages 2 or higher, duration of motor disease 5 years or longer, age >65 years, or the PIGD phenotype. Duration of motor disease will be defined as the time between onset of motor symptoms and time of entry into the study. The PIGD phenotype is defined as described previously. PD subjects with defined cholinergic deficits will be recruited as described in Project II. PD subjects will have cortical cholinergic deficits based on 5th percentile cutoff of the normal controls as defined previously.
 - 2. Stable dopaminergic replacement therapy for 3 months prior to enrollment and expected to maintain stable dopaminergic therapy for duration of study participation.
- 4.2.2 Exclusion Criteria
 - 1. Other disorders which may resemble PD with or without dementia, such as vascular dementia, normal pressure hydrocephalus, progressive supranuclear palsy, multiple system atrophy, corticobasal ganglionic degeneration, or toxic causes of parkinsonism. Prototypical cases have distinctive clinical profiles, like vertical supranuclear gaze palsy, early and severe dysautonomia or appendicular apraxia, which may differentiate them from idiopathic PD. The use of the UKPDSBRC clinical diagnostic criteria for PD will mitigate the inclusion of subjects with atypical parkinsonism and all participants will undergo [¹¹C]DTBZ PET to confirm striatal dopaminergic denervation.
 - 2. Subjects on neuroleptic, anticholinergic (trihexiphenidyl, benztropine), or cholinesterase inhibitor drugs.
 - 3. Current or previous (within last 6 months) use of any product or medication containing nicotinic agents, including use of tobacco products such as cigarettes, cigars, pipes, chewing tobacco, etc., e- cigarettes, OTC nicotine patches, chewing gum containing nicotine, or varenicline.
 - 4. Evidence of a stroke or mass lesion on structural brain imaging (MRI).
 - 5. Participants in whom magnetic resonance imaging (MRI) is contraindicated including, but not limited to, those with a pacemaker, presence of metallic fragments near the eyes or spinal cord, or cochlear implant.
 - 6. Severe claustrophobia precluding MR or PET imaging
 - 7. Subjects limited by participation in research procedures involving ionizing radiation.
 - 8. Pregnancy (test within 48 hours of each PET session) or breastfeeding.
 - 9. Significant risk of cardiovascular event.

- 10. Active, significant mood disorder.
- 11. History of seizures.
- 12. Active alcohol abuse.

4.3 Randomization and Blinding

Participants were randomized 1:1 to one of two treatment sequences: placebo followed by VCN 0.5 mg b.i.d., or VCN followed by placebo. A statistician prepared the randomization list using permuted blocks with random block sizes. The list with randomization number and treatment allocation was sent to the research pharmacy and a blinded list of randomization numbers was sent to the study coordinator. After patient consent was completed and eligibility confirmed, the coordinator assigned the next randomization number to the participant, and sent a prescription with participant ID and randomization number to the research pharmacist who dispensed the appropriate study medication. To mask drug, VCN pills or placebo were encapsulated in gelatin sheaths.

4.4 Study Assessments

4.4.1 **Primary Efficacy Assessments**

Two co-primary end points were selected: a measure of postural stability and gait function. JERK is the time-based derivative of lower trunk accelerations during standing spontaneous sway. JERK was chosen because it tracks postural instability in PD [1]. Normal pace gait speed with no distractors was chosen as prior studies indicated that neocortical cholinergic denervation is associated with slower gait speed in PD [2]. We hypothesized that VCN treated participants would ambulate faster and that VCN treatment would reduce JERK.

Postural stability was assessed with the Ambulatory Parkinson's Disease Monitoring (APDM) wearable sensor system (APDM Wearable Technologies, Inc.) using the iSWAY protocol, with participants standing on a foam pad with eyes open and eyes closed. Standard postural measures, including JERK, were assessed and calculated using the manufacturer's software (Mobility Lab Version 1). Gait analysis was performed on an 8-meter GAITRite pressure sensitive walkway (CIR Systems, Inc.) and standard parameters were analyzed using ProtoKinetics Movement Analysis Software (GAITRite version 5.09C; ProtoKinetics, LLC). Gait assessments were repeated with a dual-task protocol in which participants counted backwards by three starting at a random number (under 100) provided by the examiner.

4.4.2 Secondary Efficacy Assessments

We assessed attentional function with a Sustained Attention Test (SAT), established to reflect CNS cholinergic systems function in humans [3, 4, 5]. The SAT is performed with 2 conditions: without and with a distractor (dSAT). SAT and dSAT results are reported as the vigilance index, a measure that corrects estimates of accurate detection with penalties for false detections and not confounded by errors of omission [6]. SAT was selected as the second end point.

4.4.3 **Exploratory Efficacy Assessments**

Additional assessments of postural control, gait function and attentional function were measured as exploratory end points. Cognitive assessments were also measured for exploratory analyses.

Motor Assessments: Movement Disorder Society Unified Parkinson's Disease Rating Scale, part III (MD-UPDRSIII; "on" state); MDS-UPDRSIII postural instability and gait subscore (PIGD) subscale score (sum of items 3.1, 3.9-3.13); Gait Speed (normal pace); Gait Speed (fast pace); Gait Speed (normal pace - dual task); Gait Speed (fast pace – dual task); Postural stability measures – mean sway velocity, JERK, root mean square sway distance (RMS). To assess the effects of attentional loading, normal pace and fast pace gait were performed under dual task conditions. Dual task conditions typically lead to slower gait speed. Differences in gait speed between dual task and no dual task conditions are a measure of the attentional burden imposed by the dual task. To assess the effects of VCN on this aspect of gait performance, we compared the differences between no dual task and dual task gait speed between VCN and placebo treatment periods. We used the APDM system's iTUG

(Timed Up and Go) protocol to collect additional exploratory data.

Cognitive Assessments: For cognition, we used a general cognitive measure, the MoCA and selected tests to examine major cognitive domains but focusing on attention and executive function. MoCA; Wechsler Adult Intelligence Scale-III Digit Symbol modalities test; CVLT short term memory test; CVLT long term memory test; CVLT recognition test; D-KEFS Stroop III; D-KEFS sorting total; D-KEFS verbal fluency letters total; D-KEFS verbal fluency animals; D-KEFS Trail Making Test 4; JOLO test.

Behavioral Assessments: GDS

5 Sample Size

The sample size (planned initially at four participants per dosing group) for the VCN- $\alpha 4\beta 2^*$ nAChR occupancy study was based on logistical considerations. For the Crossover study, we calculated that 33 participants would provide at least 80% power to detect within-patient treatment differences of 0.122 m/s in gait speed and -0.131 m2/s5 for JERK, assuming within-participant correlation of > 0.64 and > 0.72, respectively, using a paired t-test and a two-sided Type I error of 0.025 (Bonferoni adjustment for co-primary endpoints). This approach is conservative given our analysis method uses mixed effects models. Estimates for treatment differences were based on Bohnen et al. [2] for normal pace gait speed and Mancini et al. for JERK [7].

6 General Analysis Considerations

6.1 Timing of Analyses

The final analysis will be performed after all randomized participants have completed their 9-week visit or dropped out prior to their 9-week visit, all corresponding data have been entered, cleaned, locked and unblinded as per the data coordinating center's standard operating procedures. This statistical analysis plan document was finalized prior to the database lock and unblinding.

6.2 Analysis Populations

All randomized participants will be used in the analyses of subject disposition.

6.2.1 Intention to Treat Population

The main analysis set for efficacy is the intention to treat (ITT) population, defined as all participants randomized.

6.2.2 Compliant Population

A compliant population is used for sensitivity analyses of the efficacy end points. It is defined as the ITT population, excluding all participants who have major protocol deviations. Major protocol deviations are defined as eligibility criteria violations for which no exemption was granted, and without evidence of significant increases in VCN plasma levels between placebo and VCN treatment periods.

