We propose subacute (days) VCN administration and focus on hypocholinergic PD subjects. Because repeated  $\alpha 4\beta 2^*$  nAChR stimulation, as would be experienced by chronically treated patients, induces functional receptor upregulation, assessing  $\alpha 4\beta 2^*$  nAChR occupancy with a single VCN dose in VCN naïve subjects will be misleading. Moreover, a VCN dose that produces high percent receptor occupancy in a VCN naïve subject may exhibit considerably less  $\alpha 4\beta 2^*$  nAChR occupancy in subjects exposed repeatedly to VCN and with  $\alpha 4\beta 2^*$  nAChR upregulation. It might be scientifically interesting to include normocholinergic PD subjects, but safety concerns hinder this approach. In our model (**Overview; Project I** data), dopaminergic striatal deficits result in compensatory "loading" of other brain systems. Normocholinergic PD subjects depend on increased cholinergic neurotransmission to compensate for striatal dysfunction, placing them at increased risk of adverse events resulting from reduced cholinergic signaling (32,46). VCN is a partial agonist with an efficacy of approximately 40% of ACh. In normal individuals, VCN produces measurable improvements on cognitive tests

(79,88), but in normocholinergic PD subjects, VCN may interfere sufficiently with  $\alpha 4\beta 2^*$  nAChR mediated compensation to produce functional impairments, including cognitive impairment and/or diminished balance, including damaging falls. It is not feasible to recruit sufficient subjects to do these experiments in an inpatient setting, which would be required to mitigate these potential side effects. For these reasons, we will not expose normocholinergic PD subjects to VCN. Beyond these important safety concerns, adding study groups to the proposed experiments would reduce statistical power for a fixed sample size, increasing the Ns required for a valid study beyond that which can be supported by funds available for Udall Center studies.

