7.1 Subject Disposition

The number of participants approached for study participation, the number consented and the number who did not consent (including reasons: screen failures, refusals) will be summarized in a CONSORT diagram. The number of participants who dropped out prior to randomization, and the reasons for dropout, will be summarized. The number randomized and treated and the number who dropped out by weeks 3, 6, and 9 will be provided, as well as the number in each of the analysis populations (i.e., ITT, Compliant, Safety). Reasons for post-treatment dropout will be provided.

7.2 **Protocol Deviations**

Major protocol deviations that exclude a patient from the Compliant Per Protocol Population are described in section 8.3.2. A listing of protocol deviations that exclude participants from the Compliant Population will be provided. A listing of participants who receive exemptions for study eligibility will also be provided.

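### The Compliant Population is defined by whether an exemption was granted, not by criteria met, so the eligibility-restricted sensitivity set can keep participants outside the target population

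*SAP*

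**What the plan says.** SAP 6.2.1 sets the primary analysis: "The main analysis set for efficacy is the intention to treat (ITT) population, defined as all participants randomized". SAP 6.2.2 then adds a second efficacy set: "A compliant population is used for sensitivity analyses of the efficacy end points". Of that set it says: "It is defined as the ITT population, excluding all participants who have major protocol deviations". Major deviations are defined in one sentence with two parts. The first covers "eligibility criteria violations for which no exemption was granted". The second follows directly: "and without evidence of significant increases in VCN plasma levels between placebo and VCN treatment periods".

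SAP 7.2 shows that exemptions are foreseen and says how they are reported: "A listing of participants who receive exemptions for study eligibility will also be provided". It also sends the reader elsewhere for the definition: "Major protocol deviations that exclude a patient from the Compliant Per Protocol Population are described in section 8.3.2". No section 8.3.2 appears in the SAP text supplied; the definition stands in 6.2.2.

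SAP 8.1 runs the primary, secondary and key efficacy endpoints in two sets only, ITT and Compliant.

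The criteria that define the target population are in SAP 4.2 and in the protocol's inclusion and exclusion lists. They include a cortical cholinergic deficit by the 5th-percentile cut-off, stable dopaminergic therapy, no anticholinergic or cholinesterase inhibitor, and no nicotinic agent within six months. The protocol's section on overall rationale adds: "For these reasons, we will not expose normocholinergic PD subjects to VCN".

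**The concern.** An exemption is permission to enrol. It does not change whether the participant has the biology under test or is free of a competing cholinergic or nicotinic drug. The hypothesis concerns PD patients with a cholinergic deficit, and the Compliant Population is the only efficacy set that restricts on eligibility. If exempted participants sit in both ITT and Compliant, no planned analysis shows whether the result holds among those who met the defining criteria.

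Membership also turns on a decision that the documents do not describe. Neither says which criteria may be waived, who grants an exemption, when, or whether that person is blinded. SAP 4.3 says only that eligibility was confirmed before a randomization number was assigned. The one explicit discretion over eligibility in the protocol text supplied concerns a depression-scale score above 5.

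**Working it through.** **Step 1: reading the definition.** The set is ITT minus participants with a major deviation. Take a participant who failed the cholinergic cut-off but holds an exemption.

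- Eligibility part: an exemption was granted, so there is no major deviation on this ground.
- Plasma part joined by *and*, read literally: exclusion needs both an unexempted violation and no plasma rise. The exempted participant stays whatever the plasma result. An ineligible participant without an exemption also stays if a plasma rise is shown.
- Plasma part read as *or*: the exempted participant stays whenever a plasma rise is shown.

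On either reading, an exempted participant who took the drug is kept. The listing in SAP 7.2 discloses this but does not change the set.

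**Step 2: illustration of size.** The rule carries no figure of its own to reproduce. From SAP section 5 I take n = 33, a paired t-test and two-sided 0.025. The stated power is at least 80%; I set it at exactly 80%.

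Power = P(T > t_crit), where T is noncentral t with n − 1 degrees of freedom and noncentrality dz × √n. With n = 33, t_crit = 2.352. Solving for 80% gives dz = 0.559 (noncentrality 0.559 × √33 = 3.21).

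Assumptions: k exempted participants have zero varenicline effect, and the SD of paired differences is unchanged. The documents do not give k, so a range is shown.

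- Kept: effect multiplied by (33 − k)/33, with n = 33.
- Removed: full effect, with n = 33 − k.

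| k | Estimate, share of true size | Power if kept | Power if removed | Difference (points) |
|---|---|---|---|---|
| 0 | 100% | 80% | 80% | 0 |
| 1 | 32/33 = 97% | 77% | 79% | about 1 |
| 2 | 31/33 = 94% | 74% | 77% | about 3 |
| 3 | 30/33 = 91% | 71% | 75% | about 4 |
| 4 | 29/33 = 88% | 68% | 74% | about 6 |

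Differences are taken before rounding. For gait speed, the protocol's 0.112 m/s becomes 0.109, 0.105, 0.102 and 0.098 m/s for k = 1 to 4. SAP section 5 gives 0.122 m/s, which becomes 0.118, 0.115, 0.111 and 0.107 m/s. The percentage shrinkage is the same.

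The relevant comparison is kept against removed, because removal also loses sample size. Setting the kept column against 80% would charge the rule with about 3, 6, 9 and 12 points, which is too much.

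**The case against.** The strongest reply is that this is a definitional choice in a secondary set. The primary estimate, its alpha and the decision rule do not depend on it. SAP 6.1 says the plan was finalized before lock and unblinding, and 6.2.2 never says that the set isolates people who met every criterion. All of that stands, and it limits the weight of the point.

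Two stronger readings are tempting and should be set aside. A reader might infer that participants outside the target population were enrolled under exemptions. The documents do not show that any exemption was granted, and a planned listing may turn out empty. A reader might also infer that the SAP contradicts the protocol's commitment on normocholinergic patients. It does not: the SAP nowhere says that the cholinergic criterion may be waived. It only fails to protect that criterion within this set. Nor can one conclude that no exemption procedure exists, since the protocol places its general eligibility criteria in the Clinical Resource Core and Project II documents, which are not supplied.

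SAP 8.1 also adds baseline cortical cholinergic denervation as a covariate for the gait speed endpoints, so cholinergic status is examined elsewhere. That is adjustment rather than restriction, it does not name JERK, and it does not address excluded drugs.

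Finally, excluding every exempted participant would be too broad. An exemption for claustrophobia or an MRI contraindication has no evident bearing on gait response. This objection stands, and the fix takes account of it.

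**Conclusion.** The point holds as a cheap improvement to a sensitivity analysis. As written, SAP 6.2.2 lets an exemption decide who counts as compliant, and a participant who failed a hypothesis-defining criterion can remain in the one efficacy set that restricts on eligibility. The primary ITT result is not affected.

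If 1 to 4 such participants were kept among 33, the estimate would shrink by 3 to 12% and power would be about 1 to 6 points lower than if they were removed. Those figures rest on zero effect in exempted participants, an unchanged SD, a set of 33 and an assumed number of exemptions. With no exemptions, or only exemptions on criteria unrelated to response, the consequence is nil.

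**What to change.** Redefine the Compliant Population in SAP 6.2.2 by criteria actually met. Exclude any participant who:

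- failed a population-defining or response-relevant eligibility criterion, whether or not exempted (name them: the cortical cholinergic cut-off, the excluded anticholinergic, cholinesterase-inhibitor and nicotinic agents, and stable dopaminergic therapy); **or**
- lacks evidence of a varenicline plasma increase between the placebo and varenicline periods.

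Deleting the exemption phrase alone is not enough. With the literal *and* left in place, an ineligible participant with a plasma rise would still stay. Keep the exemption listing in 7.2, and point its cross-reference to the section that holds the definition.

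The cost is a few lines of SAP text and possibly a few participants in the sensitivity set. If unblinding has already occurred, leave the planned set as it is and report the redefined one as a labelled additional sensitivity analysis.
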